2.5.3 Handling of intercurrent events

Non-response imputation (NRI) approach will be applied to missing post-vaccination antibody assay regardless of intercurrent events.

NRI is a conservative imputation method for dichotomous variables. NRI assumes that a participant is a treatment failure if the participant discontinues the study prematurely. Hence, for missing data the primary endpoint will be imputed as “No”. Refer to [Section 5.1.3.3](#).

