### 5.1 Inclusion criteria

Participants eligible for inclusion in Cohort 1 of this study must meet **all** of the following criteria:

1. Signed informed consent must be obtained prior to participation in the study
2. Age 18-55 years old inclusive at Screening
3. Diagnosis of relapsing MS by 2017 revised McDonald criteria
4. Must be willing to comply with the study schedule
5. Will be receiving an mRNA COVID-19 vaccine (Pfizer or Moderna vaccine) at least two weeks prior to starting ofatumumab
6. Eligible to receive and plan to be started on ofatumumab according to the approved labeling
7. Pre-ofatumumab serology with Hepatitis B testing not indicative of active or latent infection
8. Total serum immunoglobulin IgG  $\geq 400$  mg/dl at Screening

Participants eligible for inclusion in Cohort 2 of this study must meet **all** of the following criteria:

1. Signed informed consent must be obtained prior to participation in the study
2. Age 18-55 years old inclusive at Screening
3. Diagnosis of relapsing MS by 2017 revised McDonald criteria
4. Must be willing to comply with the study schedule
5. Will be receiving an mRNA COVID-19 vaccine (Pfizer or Moderna vaccine)
6. Currently on commercially prescribed ofatumumab for  $\geq 4$  weeks for the treatment of RMS
7. Pre-ofatumumab serology with Hepatitis B testing not indicative of active or latent infection
8. Total serum immunoglobulin IgG  $\geq 400$  mg/dl at Screening

Participants eligible for inclusion in Cohort 3 of this study must meet **all** of the following criteria:

1. Signed informed consent must be obtained prior to participation in the study
2. Age 18-55 years old inclusive at Screening
3. Diagnosis of relapsing MS by 2017 revised McDonald criteria

4. Must be willing to comply with the study schedule
5. Will be receiving an mRNA COVID-19 vaccine (Pfizer or Moderna vaccine)
6. Currently on commercially prescribed interferon or glatiramer acetate for  $\geq 4$  weeks for the treatment of RMS
7. Total serum immunoglobulin IgG  $\geq 400$ mg/dl at Screening

Participants eligible for inclusion in Cohort 4 of this study must meet **all** of the following criteria:

1. Signed informed consent must be obtained prior to participation in the study
2. Age 18-55 years old at Screening
3. Diagnosis of relapsing MS by 2017 revised McDonald criteria
4. Must be willing to comply with the study schedule

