### **9.1.2 Discontinuation from study**

Discontinuation from study is when the participant permanently stops receiving the study treatment, and further protocol-required assessments or follow-up, for any reason.

Participants must be discontinued from the study under the following circumstances:

- Failure to receive a complete COVID-19 mRNA (Pfizer or Moderna) vaccination course (2 doses)
- IgG  $\leq$  400mg/dl

If the participant agrees, a final evaluation at the time of the participant's study discontinuation should be made as detailed in the assessment table under the End of Study Visit (refer to [Section 8](#)).

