2.2 Analysis sets

The Safety Analysis Set (SAF) comprises all participants who signed informed consent and met all entry criteria.

Unless otherwise specified the SAF will be used for all summary tables and listings.

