2.5 Analysis supporting primary objective(s)

The primary objective of this study is to characterize those achieving immune response after receiving a full course (2 doses) vaccination with a non-live mRNA COVID-19 vaccine (Pfizer or Moderna vaccine) in participants treated with ofatumumab 20 mg s.c. once monthly. This will be achieved by estimating the immune response rate using the SAF.

An immune responder is a participant achieving immune response as defined by a positive SARS-CoV-2 qualitative IgG antibody assay after full course (2 doses) vaccination.

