2.5.4 Handling of missing values not related to intercurrent event

NRI approach will be applied to missing post-vaccination antibody assay.

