5.1.3.3 Other imputations

Non-response imputation

NRI assumes that a participant is a non-responder if there are no valid immune response assessments after receiving both doses of the vaccine. Hence, for missing data the primary endpoint of achieving immune response as defined by a positive SARS-CoV-2 qualitative IgG antibody assay ≥ 14 days after full course (2 doses) vaccination (yes/no) will be imputed as “No”.

MS relapse date imputation

The following algorithm will be used to estimate relapse start dates for which only partial information is known. Note that “index date” refers to the date of Visit 1 (Screening).

Missing day only:

- The first day of the month will be assigned to the missing day. In case the relapse start date occurs in the same month as the index date, the relapse start date will be imputed as the index date.

The following algorithm will be used to estimate relapse stop dates for which only partial information is known.

Missing day only:

- The last day of the month will be assigned to the missing day or truncated to have a maximum duration of 90 days.

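### Cohort 1–3 participants who never complete two vaccine doses are counted as vaccine non-responders in the primary analysis

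*SAP*

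**What the plan says.** - **Analysis set.** SAP 2.2: "The Safety Analysis Set (SAF) comprises all participants who signed informed consent and met all entry criteria". Protocol 12.1 defines its Safety Set in the same way. Receipt of vaccine is not a condition.
- **Primary analysis.** SAP 2.5, on the primary objective: "This will be achieved by estimating the immune response rate using the SAF". Protocol 12.4 also names the Safety Set.
- **Entry to Cohorts 1–3.** The vaccination criterion in Protocol 5.1 looks forward: "Will be receiving an mRNA COVID-19 vaccine (Pfizer or Moderna vaccine". Cohorts 4–6, by contrast, must already have completed two doses.
- **Failure to complete.** Protocol 9.1.2 lists among the grounds for mandatory study discontinuation: "Failure to receive a complete COVID-19 mRNA (Pfizer or Moderna) vaccination course (2 doses".
- **Imputation.** In SAP 2.5.3 the non-response imputation (NRI) "approach will be applied to missing post-vaccination antibody assay regardless of intercurrent events". The same section gives the rationale: "NRI assumes that a participant is a treatment failure if the participant discontinues the study prematurely". SAP 2.5.4 repeats the rule for other missing values: "NRI approach will be applied to missing post-vaccination antibody assay". SAP 5.1.3.3 words the trigger differently: "NRI assumes that a participant is a non-responder if there are no valid immune response assessments after receiving both doses of the vaccine".
- **Endpoint and estimand.** SAP 2.5.1 defines response as a positive assay at least 14 days after both doses. It describes the Cohort 1–3 populations as people who will receive a full course. The intercurrent events named are discontinuation of treatment or study, and death.

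**The concern.** The clinical question is whether people treated with ofatumumab respond to the vaccine. A participant who did not receive the full course carries no information on response to a full course, yet the plan's rules together make that participant a failure to respond. The penalty can arise only where people enter unvaccinated. It can touch Cohort 1, the Cohort 2 part of group 2+4, the Cohort 3 part of group 3+5, and the overall row, but not Cohort 6.

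Two things are at stake. The reported rate mixes vaccine uptake with immune response. And the groups are not treated alike: the protocol summary sets ofatumumab response against participants on interferon or glatiramer acetate, and a depressed reference rate would make ofatumumab look better by comparison. The direction of any net distortion cannot be known in advance.

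**Working it through.** **1. The plan's own figures.** The sample-size section gives half-widths of 20.1%, 19% and 17.5% for n = 20. With 1.96 × √(p(1 − p)/20):

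- p = 0.70: 20.08%
- p = 0.75: 18.98%
- p = 0.80: 17.53%

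These match. The enrolment figure is 20 × 1.10 = 22. The precision statement therefore lets drop-outs leave the denominator (22 becomes 20), whereas NRI on the SAF keeps all 22 in it.

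**2. Tracing a non-completer.** Take a Cohort 1–3 participant who consents, meets all entry criteria and receives no dose or one dose.

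- In the SAF? Yes: consent and eligibility suffice.
- In the study? No: discontinuation is mandatory under Protocol 9.1.2.
- Able to have a primary result? No. In SAP Tables 2 and 5 the 14-day window opens the day after dose 2, and assays between the doses are given no analysis visit.
- Scored? As a non-responder, because NRI covers every missing post-vaccination assay whatever the intercurrent event.

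The same trace cannot be run in Cohorts 4–6, because two completed doses are an entry criterion.

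**3. Size per non-completer.** Let p be the true response rate among the fully vaccinated and m the number of non-completers in a group of 22. The expected reported rate is p × (22 − m)/22, and the shift is p × m/22. The documents give no value for m, so the table shows a range of assumptions.

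| m | shift, p = 70% | shift, p = 75% | shift, p = 80% |
|---|---|---|---|
| 0 | 0 | 0 | 0 |
| 1 | −3.2 | −3.4 | −3.6 |
| 2 | −6.4 | −6.8 | −7.3 |
| 3 | −9.5 | −10.2 | −10.9 |
| 4 | −12.7 | −13.6 | −14.5 |

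Shifts are in percentage points. For m = 2 and p = 75%: 0.75 × 20/22 = 68.2%. In counts with exact 95% intervals, 15 responders give 15/20 = 75.0% (50.9 to 91.3) among the vaccinated, and 15/22 = 68.2% (45.1 to 86.1) under the plan. Values of m = 3 or 4 (13.6% and 18.2% of 22) exceed the planned 10% drop-out.

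**4. Dependence on recruitment mix.** In a pooled group, let k of the 22 come from the vaccine-naive cohort and let a fraction f of those k not complete. If p is the same in both cohorts, the expected shift is p × f × k/22. With p = 75% and f = 10% (an assumption, borrowed from the drop-out allowance):

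- k = 22: 0.75 × 0.10 × 22/22 = 7.5 points
- k = 11: 0.75 × 0.10 × 11/22 = 3.75 points
- k = 0: no shift

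The same vaccine response and the same completion behaviour thus give different reported rates according to who was recruited.

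**The case against.** The strongest defence is that this is a pre-specified, composite-type choice. Study discontinuation is a named intercurrent event, an incomplete course causes discontinuation, Protocol 12.4.3 and 12.4.4 already prescribe the imputation, and the SAP calls it conservative. An observed-case analysis is planned (Protocol 12.4.6, SAP 2.5.6), and SAP 2.3.1 lists discontinued participants with their primary reason. Readers will therefore see an estimate without these participants.

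Part of this stands: the rule is declared in advance, and the supplementary analysis limits the harm. It does not remove the mismatch. The endpoint and the Cohort 1–3 populations presuppose a full course, and incomplete vaccination is not itself named as an intercurrent event. The observed-case analysis also drops vaccinated participants with a missing assay, so the gap between the two estimates does not isolate the effect.

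Three stronger readings are tempting, and the documents do not support them.

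- **That SAP 2.5.3 turns a positive Visit 4 result into a failure if the participant later drops out.** The sentence on premature discontinuation is a general rationale. It stands between two statements that confine imputation to missing data, and SAP 5.1.3.3 has the same limit. An observed result is not overwritten.
- **That a missed Visit 4 with a valid later assay is left undecided.** SAP 1.1 fixes the primary time point at Visit 4 for Cohorts 1–3. The windows close the 14-day visit at Day 64 or 71 (Cohort 1) and Day 119 or 126 (Cohorts 2 and 3), and Day 202 or 209 maps to the 180-day visit. The primary result is missing and imputed. What remains is loose wording in 5.1.3.3, which speaks of no valid assessment at all and presupposes both doses.
- **That a loss of about 7 points is expected.** The 10% is an overall drop-out allowance for a study of 382 to 389 days, not a rate of incomplete vaccination. In the pooled groups, two non-completers would both have to come from the vaccine-naive cohort.

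**Conclusion.** The concern holds for the primary estimate in Cohort 1, in groups 2+4 and 3+5, and in the overall row. As written, the plan counts non-completers of vaccination as vaccine non-responders, so these rates are biased downward as estimates of response after a full course. The secondary response and conversion analyses use the same imputation (SAP 2.6.3 and 2.6.4) and are exposed in the same way.

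The size rests on an assumption, since the number of non-completers is not given: about 3.4 points per non-completer at a true 75% in a group of 22, and nothing if everyone completes. Using the whole 10% allowance, 6.8 points, is an upper case within the plan's own drop-out figure. The two descriptions of NRI need aligning, but they are not shown to produce different primary results for participants who received both doses.

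**What to change.** In Protocol 12.4 and SAP 2.5 and 2.6, base the response analyses on SAF participants who received both doses. Within that set, keep NRI: at each analysis visit, a participant with no valid assay in the window counts as a non-responder. Report by cohort the number who did not complete vaccination. Safety summaries stay on the full SAF.

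Align SAP 2.5.3 and 5.1.3.3, and 2.6.3 with them, so that the trigger is a missing valid assay at the given analysis visit. Replace the sentence about premature discontinuation, and state that observed results stand.

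An acceptable alternative is to keep the SAF and name incomplete vaccination as an intercurrent event with its own stated strategy, in Protocol 2.1 and SAP 1.2.1 and 2.5.1.

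Either way, SAP Section 4, which now reports no departures from the protocol's analyses, should record the change.

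No new data are needed, because the schedules for Cohorts 1–3 already include a vaccine administration form around each dose. The cost is a slightly smaller denominator in Cohorts 1–3 and a documented change to the analysis set that the protocol specifies. With no randomisation and no hypothesis test, no randomised comparison or error rate is put at risk.

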2.5.4 Handling of missing values not related to intercurrent event

NRI approach will be applied to missing post-vaccination antibody assay.

2.5.5 Sensitivity analyses

There are no sensitivity analyses of the primary endpoint planned for this study.

2.5.6 Supplementary analyses

A supplemental analysis of the primary endpoint will be performed using an observed case approach (completers) by using valid assessments of antibody assay without imputation of missing data.

In addition, the primary analysis will be repeated using data from Cohort 6 participants and any participants in Cohorts 1 – 5 who received an mRNA booster during the study. Missing post-vaccination antibody assay will be handled according to the NRI approach.

For each supplemental analysis the number and percentage of responders will be presented by cohort group and overall. The 2-sided 95% CI for the proportion of responders will be calculated using an exact method ([Clopper and Pearson, 1934](#)).

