#### 1. Screening Period:

Participants will enter a Screening Period of up to 7 days to assess eligibility requirements. Participants in Cohort 1, 2, 4 and 6 without Hepatitis B virus (HBV) and total serum immunoglobulin results within the past 6 months prior to screening will require central labs drawn. Participants with Hepatitis B virus (HBV) and total serum immunoglobulin results within the specified inclusion range the past 6 months prior to screening will not require the labs to be drawn.

Participants in Cohort 3 and 5 without total serum immunoglobulin results within the past 6 months prior to screening will require central labs drawn. Participants with total serum immunoglobulin results within the specified inclusion range the past 6 months prior to screening will not require the labs to be drawn.

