### **Special guidance regarding the scheduling of visits for Cohorts 1, 2 and 3**

- The study site will need to perform Vaccine Status Check-ins (make remote contact with participant) to confirm when the 1st and 2nd COVID-19 vaccinations are scheduled in order to schedule Visit 4.
- The date of the 2nd COVID-19 vaccine dose will determine the date of Visit 4 and all other remaining study visits.
- Visits 2 and 3 should always occur prior to administration of the mRNA vaccine.
- The Visit 4 lab samples should be collected 14 days after a participant has received their 2nd COVID-19 vaccine dose.

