Cohort 2: Relapsing MS participants receiving a full course (2 doses) of a non-live COVID-19 mRNA vaccine ≥4 weeks after ofatumumab start.

Will continue taking their prescribed ofatumumab as per their current dosing schedule.

Cohort 3: Relapsing MS participants receiving a full course (2 doses) of a non-live COVID-19 mRNA vaccine ≥4 weeks after start of prescribed interferon or glatiramer acetate.

Will continue administration of their prescribed interferon or glatiramer acetate as per their current dosing schedule.

Cohort 4: Relapsing MS participants having completed a full course (2 doses) of a non-live COVID-19 mRNA vaccine ≥4 weeks after ofatumumab start.

Will continue taking their prescribed ofatumumab as per their current dosing schedule.

Cohort 5: Relapsing MS participants having completed a full course (2 doses) of a non-live COVID-19 mRNA vaccine ≥4 weeks after glatiramer acetate or interferon start.

Will continue taking their prescribed glatiramer acetate or interferon as per their current dosing schedule.

Cohort 6: Relapsing MS participants having completed a full course (2 doses) of a non-live COVID-19 mRNA vaccine ≥4 weeks after ofatumumab start and having received a booster ≥14 days prior to screening.

Will continue taking their prescribed ofatumumab as per their current dosing schedule.

Study completion

According to the protocol, study completion is defined as when the last participant completes the end of study (EOS) visit. Participants who discontinue study treatment or who decide they do not wish to participate in the study further should NOT be considered withdrawn from the study UNLESS they withdraw their consent. Where possible, they should return for the EOS visit.

Study design schematics for Cohorts 1, 2 and 3 are shown in Figures 1, 2, 3 and 4. Study design schematics for Cohorts 4, 5 and 6 are shown in Figures 5 and 6.

Figure 1 Study Design (Cohort 1, Pfizer)

[figure not shown]

Figure 2 Study Design (Cohort 1, Moderna)

[figure not shown]

Figure 3 Study Design (Cohorts 2 and 3, Pfizer)

[figure not shown]

Figure 4 Study Design (Cohorts 2 and 3, Moderna)

[figure not shown]

Figure 5 Study Design (Cohorts 4, 5 and 6, Pfizer)

[figure not shown]
[figure not shown]

Figure 6 Study Design (Cohorts 4, 5 and 6, Moderna)

Primary analysis time point

The primary analysis time point is Visit 4 for Cohorts 1, 2 and 3, and Visit 2 for Cohorts 4, 5 and 6.

Interim analysis

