2.4.1.1 Visit windows

Visit windows will be used for data that are summarized by visit; they are based on the study evaluation schedule and comprise a set of days around the nominal visit day. When visit windows are used, all visits, including unscheduled visits, will be re-aligned (i.e., they will be mapped into one of the visit windows). In the case of major deviations from the visit schedule, or due to unscheduled visits, several assessments for a participant may fall in a particular visit window (either scheduled or unscheduled). Approaches for handling multiple assessments in a visit window are outlined below.

The following steps are used to determine the cut-offs for visit windows:

- The visit window associated with the previous assessment ends prior to the middle point; the visit window associated with the latter assessment begins after the middle point. In case the middle point is an exact study day, it will belong to the previous assessment.
- The visit window of the first post-vaccination assessment starts the day after the second dose of the COVID-19 vaccine for Cohorts 1 – 5, and the day after the COVID-19 vaccine booster for Cohort 6, unless otherwise specified.

Tables 2 – 10 provide visit windows for applicable parameters.

Table 2**Cohort 1 visit windows for SARS-CoV-2 qualitative antibody / CD19+ B cells / T cell**

Analysis visit	Nominal time point	Scheduled visit day (target study day)	Visit window (study days)
Pfizer vaccine:			
Pre-vaccination	Day 1	1	≤1
14 days post-vaccination	Day 36	36	(vaccine day + 1) to 64
70 days post-vaccination	Day 92	92	65 to 147
180 days post-vaccination	Day 202	202	148 to 247
270 days post-vaccination	Day 292	292	248 to 337
360 days post-vaccination	Day 382	382	≥338
Moderna vaccine:			
Pre-vaccination	Day 1	1	≤1
14 days post-vaccination	Day 43	43	(vaccine day + 1) to 71
70 days post-vaccination	Day 99	99	72 to 154
180 days post-vaccination	Day 209	209	155 to 254
270 days post-vaccination	Day 299	299	255 to 344
360 days post-vaccination	Day 389	389	≥345

Note:

- Pre-vaccination and study day are derived as outlined in [Section 2.1.1](#).
- Vaccine day is the study day of the second dose of the COVID-19 vaccine.
- Assessments performed between the first and second doses of the COVID-19 vaccine are not assigned an analysis visit.

Table 3**Cohort 1 visit windows for serum immunoglobulin (IgG, IgM)**

Analysis visit	Nominal time point	Scheduled visit day (target study day)	Visit window (study days)

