Pfizer vaccine:			
Pre-vaccination	Day 1	1	≤1
14 days post-vaccination	Day 36	36	(vaccine day + 1) to 64
70 days post-vaccination	Day 92	92	65 to 147
180 days post-vaccination	Day 202	202	148 to 292
360 days post-vaccination	Day 382	382	≥293
Moderna vaccine:			
Pre-vaccination	Day 1	1	≤1
14 days post-vaccination	Day 43	43	(vaccine day + 1) to 71
70 days post-vaccination	Day 99	99	72 to 154
180 days post-vaccination	Day 209	209	155 to 299
360 days post-vaccination	Day 389	389	≥300

Note:

- Pre-vaccination and study day are derived as outlined in [Section 2.1.1](#).
- Vaccine day is the study day of the second dose of the COVID-19 vaccine.
- Assessments performed between the first and second doses of the COVID-19 vaccine are not assigned an analysis visit.

[figure not shown]

Table 5**Cohorts 2 and 3 visit windows for SARS-CoV-2 qualitative antibody / CD19+ B cells (Cohort 2 only) / T cell**

Analysis visit	Nominal time point	Scheduled visit day (target study day)	Visit window (study days)
Pfizer vaccine:			
Pre-vaccination	Day 1	1	≤1
14 days post-vaccination	Day 36	36	(vaccine day + 1) to 119
180 days post-vaccination	Day 202	202	120 to 247
270 days post-vaccination	Day 292	292	248 to 337
360 days post-vaccination	Day 382	382	≥338
Moderna vaccine:			
Pre-vaccination	Day 1	1	≤1
14 days post-vaccination	Day 43	43	(vaccine day + 1) to 126
180 days post-vaccination	Day 209	209	127 to 254
270 days post-vaccination	Day 299	299	255 to 344
360 days post-vaccination	Day 389	389	≥345

Note:

- Pre-vaccination and study day are derived as outlined in [Section 2.1.1](#).
- Vaccine day is the study day of the second dose of the COVID-19 vaccine.
- Assessments performed between the first and second doses of the COVID-19 vaccine are not assigned an analysis visit.

Table 6**Cohorts 2 and 3 visit windows for serum immunoglobulin (IgG, IgM)**

Analysis visit	Nominal time point	Scheduled visit day (target study day)	Visit window (study days)
Pfizer vaccine:			
Pre-vaccination	Day 1	1	≤1
180 days post-vaccination	Day 202	202	(vaccine day + 1) to 292
360 days post-vaccination	Day 382	382	≥293
Moderna vaccine:			
Pre-vaccination	Day 1	1	≤1
180 days post-vaccination	Day 209	209	(vaccine day + 1) to 299
360 days post-vaccination	Day 389	389	≥300

Note:

- Pre-vaccination and study day are derived as outlined in [Section 2.1.1](#).
- Vaccine day is the study day of the second dose of the COVID-19 vaccine.

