- Assessments performed between the first and second doses of the COVID-19 vaccine are not assigned an analysis visit.

Table 8**Cohorts 4, 5 and 6 visit windows for SARS-CoV-2 qualitative antibody / CD19+ B cells (Cohorts 4 and 6 only) / T cell**

Analysis visit	Nominal time point	Scheduled visit day (target study day)	Visit window (study days)
Pfizer vaccine:			
14 days post-vaccination	Day 1	1	(vaccine day + 1) to 1
180 days post-vaccination	Day 202	202	2 to 247
270 days post-vaccination	Day 292	292	248 to 337
360 days post-vaccination	Day 382	382	≥338
Moderna vaccine:			
14 days post-vaccination	Day 1	1	(vaccine day + 1) to 1
180 days post-vaccination	Day 209	209	2 to 254
270 days post-vaccination	Day 299	299	255 to 344
360 days post-vaccination	Day 389	389	≥345

Note:

[figure not shown]
- Study day is derived as outlined in [Section 2.1.1](#).
- Vaccine day is the study day of the second dose of the COVID-19 vaccine for Cohorts 4 and 5, and the study day of the COVID-19 vaccine booster for Cohort 6.

Table 9 **Cohorts 4, 5 and 6 visit windows for serum immunoglobulin (IgG, IgM)**

Analysis visit	Nominal time point	Scheduled visit day (target study day)	Visit window (study days)
Pfizer vaccine:			
14 days post-vaccination	Day 1	1	(vaccine day + 1) to 1
180 days post-vaccination	Day 202	202	2 to 292
360 days post-vaccination	Day 382	382	≥293
Moderna vaccine:			
14 days post-vaccination	Day 1	1	(vaccine day + 1) to 1
180 days post-vaccination	Day 209	209	2 to 299
360 days post-vaccination	Day 389	389	≥300

Note:

- Study day is derived as outlined in [Section 2.1.1](#).
- Vaccine day is the study day of the second dose of the COVID-19 vaccine for Cohorts 4 and 5, and the study day of the COVID-19 vaccine booster for Cohort 6.

Multiple assessments

When there are multiple assessments in a particular visit window, the rules outlined below are applied to select one value “representing” the participant in summary statistics for that visit window. All assessments will be displayed in listings.

- **Pre-vaccination (only applicable to Cohorts 1, 2 and 3):** Pre-vaccination is derived as outlined in [Section 2.1.1](#). In situations where the same assessment is performed more than once on Study Day 1 the repeated assessment will be used.
- **Post-vaccination:** For post-vaccination visit windows, the following rules apply (unless otherwise specified):

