 - For *continuous variables*, the assessment with the study day that is closest to the target study day is selected. If two assessments are equidistant from the target study

day, the earlier assessment is selected (if one of the two equidistant assessments is an unscheduled assessment, it should be excluded from consideration).

- For *categorical variables*, the assessment with the worst result is selected.

If categorical variables are based on continuous variables, the analysis visit will be assigned to the continuous variable, and this analysis visit will be used for the derived categorical variable.

In situations where the same assessment is performed more than once on the same date the repeated assessment will be used.

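### SAP 2.5.6 analyses boosted participants at the unchanged primary time point, so on schedule its Cohort 1–5 rows cannot show a response to an in-study booster; it also leaves out Cohort 5 participants boosted only before enrolment

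*SAP*

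**What the plan says.** - **Selection.** SAP 2.5.6 repeats the primary analysis in Cohort 6 and "any participants in Cohorts 1 – 5 who received an mRNA booster during the study". SAP 2.6.6 applies the same selection to the secondary endpoints. Both use non-response imputation (NRI) for missing assays and report by cohort group and overall.
- **Time point.** SAP 1.1: "The primary analysis time point is Visit 4 for Cohorts 1, 2 and 3, and Visit 2 for Cohorts 4, 5 and 6". SAP 2.5.6 names no other.
- **Timing of those visits.** For Cohorts 1–3, protocol section 8 says: "The Visit 4 lab samples should be collected 14 days after a participant has received their" second vaccine dose. For Cohorts 4–6, Visit 2 is Study Day 1, and protocol section 3 says: "Participants will enter a Screening Period of up to 7 days to assess eligibility requirements".
- **Anchor.** In SAP 2.4.1.1 the first post-vaccination window opens after dose 2 for Cohorts 1–5 and after the booster for Cohort 6. The Table 8 note says: "Vaccine day is the study day of the second dose of the COVID-19 vaccine for Cohorts 4 and 5". In that table the first window for Cohorts 4–6 closes on Day 1.
- **Several assays in one window.** For categorical variables, "the assessment with the worst result is selected".
- **Who may be boosted.** Protocol 5.1 lets Cohort 5 enter already boosted. Protocol 12.5 places participants boosted before enrolment and those boosted during the trial in one group, to be analysed separately. Protocol 1.2 lists the effect of a booster among the study's aims, but Table 2-1 has no booster objective or endpoint.

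**The concern.** A table restricted to boosted participants will be read as showing how they responded to the booster. For Cohorts 1–5 the sample it uses was fixed by dose 2 or by entry to the study, before a later booster could act. The SAP re-anchors to the booster for Cohort 6 but does not carry this over to the other boosted participants.

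The selection rule works against the same aim. Cohort 5 participants boosted before enrolment had that booster at least 2 weeks earlier, so their Visit 2 sample is a true post-booster sample. They are outside the table unless they are boosted again in the study.

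At stake is the interpretation of the only primary-endpoint table devoted to boosted participants. The primary estimates themselves are not at stake.

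**Working it through.** **Inputs.** Target days come from protocol Tables 8-1 to 8-6 and SAP Tables 2, 5 and 8. Dose 2 is on Day 22 (Pfizer) or Day 29 (Moderna). Visit 4 for Cohorts 1–3 is on Day 36 or 43. The next antibody assay is on Day 92 or 99 (Cohort 1) and Day 202 or 209 (Cohorts 2–5). The last is on Day 382 or 389.

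**1. The plan's window ends reproduce as midpoints.**
- Cohort 1: (36 + 92)/2 = 64; (43 + 99)/2 = 71.
- Cohorts 2–3: (36 + 202)/2 = 119; (43 + 209)/2 = 126.

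**2. Cohorts 1–3 on schedule.** Visit 4 minus dose 2 is 36 − 22 = 43 − 29 = 14 days. A booster given after dose 2 is therefore less than 14 days old at Visit 4, or has not yet been given. A draw at the end of the allowed +3 days is 17 days after dose 2, so a booster 14 days earlier would have to fall within 17 − 14 = 3 days of dose 2.

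**3. Cohorts 4–5 on schedule.** The window closes on Day 1 and screening lasts at most 7 days. A booster given in screening precedes the Visit 2 sample by about 7 days at most, which is under 14. Any later booster follows the sample.

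**4. The late-draw exception, Cohorts 1–3 only.** The latest usable booster, in days after dose 2, is window end − 14 − dose-2 day.
- Cohort 1: 64 − 14 − 22 = 71 − 14 − 29 = 28 days.
- Cohorts 2–3: 119 − 14 − 22 = 126 − 14 − 29 = 83 days.

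If the Visit 4 sample is in the same window, the worst result is kept, so a negative Visit 4 result stands.

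**5. The rows of the 2.5.6 table, on schedule.**

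| Row | What it holds |
|---|---|
| Cohort 1; Cohorts 2 and 4; Cohorts 3 and 5 | No result 14 or more days after an in-study booster |
| Cohort 6 | The same participants, visit and imputation as the main table |
| Overall | A mixture of the two |

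**6. What scheduled assays could show.** This counts booster days after the primary visit, up to the last assay, that have a scheduled assay at least 14 days later. The last such day is 382 − 14 = 368 (Pfizer) or 389 − 14 = 375 (Moderna).

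| Cohorts | Booster days | Covered | Share |
|---|---|---|---|
| 1–3 (Days 37–382 or 44–389) | 346 | 332 | 96.0% |
| 4–5 Pfizer (Days 2–382) | 381 | 367 | 96.3% |
| 4–5 Moderna (Days 2–389) | 388 | 374 | 96.4% |

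These are calendar days, not participants.

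**7. Longest delay from booster to first usable assay, for boosters after the primary visit.**
- Cohort 1: Day 79 to Day 202 = 123 days (Day 79 is only 13 days before Day 92).
- Cohorts 2–3: Day 37 to Day 202 = 165 days.
- Cohorts 4–5: Day 2 to Day 202 = 200 days, or Day 2 to Day 209 = 207 days.

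**The case against.** **The time point is inferred.** The SAP says only that the primary analysis is repeated. That is so, but no other time point is given, and a programmer would apply SAP 1.1.

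**The analysis is minor.** It is supplementary, no hypothesis is tested, and no booster endpoint exists. This stands and limits the weight of the point. It does not make the table informative.

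**SAP 2.6.6 and the listings cover the gap.** In part. Later visits can hold post-booster samples, shown by time point, and every assessment is listed. But 2.6.6 does not separate pre- from post-booster samples. For Cohorts 4–5 the later windows are fixed study days counted from Visit 2; for no cohort from 1 to 5 are they counted from an in-study booster.

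**The overall row is not peculiar to this table.** True: the main analysis also pools booster-anchored Cohort 6 with the rest. The mixture is more misleading in a table defined by having been boosted.

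Four stronger readings are tempting and not supported:
- *Every Cohort 1–5 result predates the booster.* A screening-period booster in Cohorts 4–5 can precede Visit 2 by a few days, and a late or unscheduled draw in Cohorts 1–3 can follow a booster.
- *A count shows that no booster is captured.* For boosters given after the primary visit the count is zero by construction, so it is not separate evidence.
- *SAP section 4 is wrong to declare no changes.* The SAP cites protocol version 01, and the documents do not show whether that version had the sentence now in protocol 12.5. That sentence also names no endpoint or time point.
- *Booster dates will be incomplete.* Nothing says so, and protocol section 3 asks participants to bring vaccination documents. It is a precaution for the fix, not a fault found.

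**Conclusion.** The point holds and should be fixed. As written and on schedule, three of the four cohort-group rows in SAP 2.5.6 hold no result 14 or more days after an in-study booster, and the fourth repeats the main table. Separately, 2.5.6 and 2.6.6 omit Cohort 5 participants boosted only before enrolment, which differs from the current protocol 12.5.

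This rests on reading the repeated analysis as keeping the SAP 1.1 time point, and on visits held on their target days. The number of participants affected cannot be computed, because the documents do not say how many were boosted.

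A reader might infer that the primary results are biased or that the booster question is lost. Neither follows: the primary estimates are untouched, and the main tables still allow a descriptive comparison of Cohort 6 with Cohorts 2 and 4.

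**What to change.** 1. **Selection.** For the immune-response endpoint in 2.5.6 and 2.6.6, include everyone boosted before or during the study: Cohort 6, Cohort 5 boosted before enrolment, and Cohorts 1–5 boosted in the study. Do not add Cohort 5 boosted before enrolment to the immune-conversion repeat. SAP 2.1.1 limits pre-vaccination values to Cohorts 1–3, and SAP Table 1 limits the nucleocapsid definition to unboosted participants, so no definition applies and NRI would wrongly score them as non-converters.
2. **Time point.** In 2.5.6 use each participant's first valid IgG assay at least 14 days after the first booster, and report the days from booster to assay. In 2.6.6 flag each sample as pre- or post-booster.
3. **Presentation.** Show the last pre-booster result alongside where one exists. Do not pool pre- and post-booster results in one row.
4. **Missing data.** Keep NRI for those who had a scheduled assay at least 14 days after the booster but missed it. List separately those boosted too late for one (after Day 368 Pfizer or Day 375 Moderna, on target days).
5. **Dates.** Query a missing booster day before lock. If it stays missing, count a sample as post-booster only if it is at least 14 days after the last day of that month. The first-of-month rule in SAP 5.1.3 could move a booster on the 31st back 30 days, and a sample on the 15th, 16 days before the booster, would then count as 14 days after it. This matters because the schedule tables that show the Vaccine Administration Form place it only at Visits 2–3 (Cohorts 1–3) or Screening (Cohorts 4–6), so later boosters may rest on concomitant-medication records.

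**Cost.** SAP text and programming on scheduled assays; no new samples. Cells will be small: as assumed examples, the exact 95% interval is 28.4% to 99.5% for 4/5 (half-width about 36 points) and 48.2% to 97.7% for 9/11 (about 25 points). The booster-to-assay delay will vary up to the limits in step 7 of the working. It is slightly longer for a Cohort 4–5 booster given in screening, and has no upper limit for Cohort 5 boosted before enrolment.
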